1.7 Rationale and Hypothesis

Obesity and metabolic syndrome are prevalent among prostate cancer patients. Hyperinsulinemia is associated with a shorter median time to progression and median OS in patient with biochemical recurrence. Early ADT is frequently used in this patient population, with no proven benefit, which may increase mortality and morbidity.

Metformin is an inexpensive and safe drug that may have anticancer activity through

both insulin-dependent and insulin-independent mechanisms, which involve activation of adenosine monophosphate (AMP)-activated protein kinase (AMPK), inhibiting mTOR signaling pathway⁷⁷. Recent evidence suggests activation of AMPK leads to down regulation of AR⁷⁸ and inhibits xenograft growth of several PCa cell lines⁵⁴. Metformin should work better in early, castrate sensitive prostate cancer since in castration resistant disease AR signaling is increased (through amplification, mutations, and intracellular androgen stimulation) which may hamper metformin's ability to inhibit cancer growth.

Bicalutamide is a non-steroidal antiandrogen, which functions by blocking the AR. It exerts its effect predominantly through induction of a G1/S phase arrest of the cell cycle⁷⁹. Published preclinical data suggest the additive anticancer effects of combining metformin and bicalutamide in the prostate cancer patients with metabolic syndrome and possible synergistic activity with antiandrogens: in AR-positive cells, this effect appeared to be mediated by reducing proliferation rates by modulating the AR, whereas in AR-negative cells the combination treatment appeared to promote apoptosis.

HYPOTHESIS:

Metformin will enhance the antitumor effects of the antiandrogen bicalutamide in the setting of preserved testosterone, effectively delaying onset of metastases while preserving quality of life in overweight and obese men with castrate naïve non-metastatic prostate cancer with biochemical recurrence.

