3.0 PATIENTS SELECTION

3.1 Inclusion Criteria

- 3.1.1** Ability to understand and the willingness to sign a written informed consent.
- 3.1.2** Male 18 years or older.
- 3.1.3** Histologically or cytologically confirmed diagnosis of prostate cancer.
- 3.1.4** Patient must have had previous treatment with definitive surgery or radiation therapy or cryoablation.
- 3.1.5** Patient may have prior salvage therapy (surgery, radiation or other local ablative procedures) within 6 months prior to randomization if the intent was for cure. Prophylactic radiotherapy to prevent gynecomastia within 4 weeks prior to randomization is allowed.
- 3.1.6** Patient may have had prior neoadjuvant and/or adjuvant therapy (chemotherapy, vaccines or experimental agents) within 4 weeks prior to randomization, if the PSA rise and PSADT were documented after the testosterone level was > 150 ng/dL.
- 3.1.7** Patients may have had therapy modulating testosterone levels (such as luteinizing-hormone, releasing-hormone agonists/antagonists and antiandrogens) in the past as long as the testosterone level is > 150 ng/dL within 4 weeks of trial entry. Agents such as 5 alpha reductase inhibitors, ketoconazole, abiraterone, systemic steroids, or herbal supplements known to decrease PSA levels including any dose of Megestrol acetate, Finasteride (e.g., Saw Palmetto and PC-SPES, African pygeum extract, lycopene, alanine, glutamic acid and glycine, beta-sitosterol, lycopene, nettle root extract, quercitin, Belizian Man Vine extract, mulra puama extract and epimedium extract Campesterol, Beta- sitosterol, Stigmasterol, Sitostanol and Brassicasterol) are not permitted at any time during the period that the PSA values are being collected.
- 3.1.8** Patient must have hormone-sensitive prostate cancer as evident by a serum total testosterone level > 150 ng/dL within 12 weeks prior to randomization.
- 3.1.9** PSA must be < 30 ng/mL at study entry.
- 3.1.10** Patient must have evidence of biochemical failure after primary therapy and

subsequent progression. Biochemical failure is declared when the PSA reaches a threshold value after primary treatment and it differs for radical prostatectomy or radiation therapy.

- For radical prostatectomy the threshold for this study is $PSA \geq 0.2$ ng/mL
- For radiation therapy the threshold is a PSA rise of 2 ng/mL above the nadir PSA achieved post radiation with or without hormone therapy (2006 RTGO-ASTRO Consensus definition).

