3.2 Exclusion Criteria

3.2.1 Evidence of metastatic disease on imaging studies (CT, x-ray, and/or bone scan).

3.2.2 Diagnosis of diabetes mellitus defined as:

- Fasting blood glucose > 126 mg/dl or,
- Random blood glucose > 200 mg/dl
- Hemoglobin A1C $> 6.5\%$

- 3.2.3** Need for treatment with any conventional modality for prostate cancer (surgery, radiation therapy, and hormonal therapy).
- 3.2.4** Treatment with any investigational drug 30 days prior to randomization.
- 3.2.5** Radiation therapy within prior 6 months (prophylactic radiotherapy to prevent gynecomastia within 4 weeks prior to randomization is allowed).
- 3.2.6** Known hypersensitivity to metformin.
- 3.2.7** Prior history of lactic acidosis.
- 3.2.8** Any history of myocardial infarction in the past 12 months.
- 3.2.9** Subjects who consume more than 3 alcoholic beverages per day.
- 3.2.10** Subjects with serious intercurrent illness, including, but not limited to, ongoing or active infection, symptomatic congestive heart failure, unstable angina pectoris, cardiac arrhythmia, or other nonmalignant medical or psychiatric illness that is uncontrolled or whose control may be jeopardized by the complications of this therapy or may limit compliance with the study requirements (at the discretion of the investigator).
- 3.2.11** Patient with previous or concurrent malignancy. Exceptions are made for patients who meet any of the following conditions: Basal cell or squamous cell carcinoma of the skin or prior malignancy that has been adequately treated and patient has been continuously disease free for ≥ 2 years.
- 3.2.12** Subjects currently treated with metformin and/or bicalutamide or who have been treated with metformin and/or bicalutamide in the past 6 months.
- 3.2.13** Subjects who have taken 5 α -reductase inhibitors (finasteride or dutasteride), saw palmetto, or PC-SPES within the last 6 weeks are ineligible. Subjects will be eligible for the study after the wash out period of 6 weeks.

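### Men with prior hormone therapy can qualify on a PSA doubling time measured during testosterone recovery, because the timing rule in 3.1.6 is not carried into 3.1.7

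*Combined protocol and SAP*

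**What the plan says.** All references are to the combined protocol and SAP.

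- **3.1.6** admits men with "prior neoadjuvant and/or adjuvant therapy (chemotherapy, vaccines or experimental agents) within 4 weeks prior to randomization", on the condition "if the PSA rise and PSADT were documented after the testosterone level was > 150 ng/dL". Hormone therapy is not named.
- **3.1.7** deals with drugs that lower testosterone or block its action, used in the past, "as long as the testosterone level is > 150 ng/dL within 4 weeks of trial entry". It sets no minimum time off drug and does not mention the dates of the PSA values. Its second sentence bars a list of other PSA-lowering agents while the PSA values are being gathered. That list names neither LHRH agents nor antiandrogens.
- **3.1.8** asks every man for a "serum total testosterone level > 150 ng/dL within 12 weeks prior to randomization", again without reference to PSA dates.
- **3.1.10** sets the threshold at 0.2 ng/mL after prostatectomy. After radiation it is 2 ng/mL above a nadir that may have been reached on hormone therapy.
- **3.1.11** requires a PSADT of 3 to 12 months, computed from PSA2 and PSA3, both drawn in the 12 months before entry.
- **3.2.12** excludes men "treated with metformin and/or bicalutamide in the past 6 months". No other antiandrogen is named.
- **3.2.4** excludes "Treatment with any investigational drug 30 days prior to randomization".
- **2.2** lists the change in PSADT from before to during and after treatment as a secondary endpoint. **7.6** calls the same comparison exploratory.

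**The concern.** The protocol accepts that a PSA rise can be read as recurrence only once testosterone has recovered, and 3.1.6 says so. It attaches that condition to treatments that do not mainly act through testosterone, and leaves it off the ones that do. When androgen suppression ends, PSA can climb because testosterone is returning, whatever the tumour growth rate. A normal testosterone at entry does not show that it was normal when PSA2 and PSA3 were drawn.

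Two things are at stake. PSADT of 3 to 12 months defines the study population, so a PSADT measured during recovery admits men whose true growth rate is unknown. The same value is also the pre-study reference for the PSADT-change endpoint. If it is artificially short, PSADT will appear to lengthen on study in either arm. Because that comparison is made within each patient, randomisation does not protect it.

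For antiandrogens a testosterone check is weaker still. The hypothesis in 1.7 has the "antiandrogen bicalutamide in the setting of preserved testosterone", so a normal level does not show that such a drug has stopped acting.

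**Working it through.** **1. PSADT formula (3.1.11).** PSADT in months = 0.693 × t / [ln(PSA3) − ln(PSA2)] / 30.4375, with t in days. The PSA values below are assumed for illustration.

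- 0.3 to 0.6 ng/mL over 120 days: 0.693 × 120 / 0.6931 / 30.4375 = 3.9 months, in range.
- 0.4 to 0.8 ng/mL over 180 days: 0.693 × 180 / 0.6931 / 30.4375 = 5.9 months, in range.
- 2.5 to 4.0 ng/mL over 120 days (after radiation, assumed nadir 0.3, so threshold 2.3): 0.693 × 120 / 0.4700 / 30.4375 = 5.8 months, in range.
- 0.3 to 0.9 ng/mL over 60 days: 0.693 × 60 / 1.0986 / 30.4375 = 1.2 months, excluded.

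The formula sees only two values and an interval. It screens out the fastest rebounds but cannot tell a moderate recovery-driven rise from tumour growth.

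**2. One assumed patient against the criteria.** After prostatectomy he stopped an LHRH agonist 8 months before entry. PSA reached 0.2. PSA2 was 0.3 with testosterone 40 ng/dL, and PSA3 was 0.6, 120 days later, with testosterone 120. Testosterone at entry is 160.

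- 3.1.7 and 3.1.8: 160 > 150, met.
- 3.1.10: threshold 0.2 reached and PSA rising, met.
- 3.1.11: two rises above threshold, both within 12 months, PSADT 3.9 months, met.
- The 3.1.6 condition, had it applied: testosterone was 40 and 120 at the two PSAs, both below 150, not met.

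The one condition that would stop him is the one not attached to his treatment.

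**3. Antiandrogens.** The PSA window is 12 months and the bicalutamide exclusion is 6 months. That leaves 12 − 6 = 6 months (months 6 to 12 before entry) from which a qualifying PSA may date while the man was still on bicalutamide or had just stopped. For other antiandrogens no interval is stated.

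**4. The primary test.** Exact enumeration of section 11.1 (26 and 13 patients, then 44 and 22; continue if 13E1 − 26C1 > −52 and E1 ≥ 6; reject if 22(E1+E2) − 44(C1+C2) ≥ 88 and E1+E2 ≥ 14) gives:

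| Null rate | Type I error, plan | Recomputed | Power for +20 points, plan | Recomputed |
|---|---|---|---|---|
| 20% | 3.24% | 3.246% | 80.3% | 80.36% |
| 25% | 10.9% | 10.98% | 83.3% | 83.38% |
| 30% | 19.7% | 19.70% | 83.2% | 83.25% |

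The plan's figures reproduce, and an eligibility gap does not change them. It matters only if it moves the common response rate, and the documents give neither the share nor the response rate of such men. As an assumed range, let a share f respond at rate q in both arms, so the common rate is 0.20(1 − f) + qf.

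- f = 10%, q = 40%: 0.18 + 0.04 = 22%, type I error 5.8%.
- f = 30%, q = 60%: 0.14 + 0.18 = 32%, type I error 22.2%.
- If such men respond less often and the common rate falls to 15%: type I error 0.3%, power 68%.

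The effect could go either way.

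**5. Experimental agents.** Read literally, 3.1.6 permits them in the 28 days before randomisation, while 3.2.4 excludes investigational drugs in the preceding 30 days.

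**The case against.** The best counter-reading is that 3.1.6 already covers the case. Its testosterone condition makes little sense for chemotherapy or vaccines alone, so hormonal neoadjuvant or adjuvant treatment may have been intended. That is plausible as intent. But the parenthesis omits hormone therapy and 3.1.7 handles it separately with a different condition, so a site applying the text as written would not enforce it.

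The barred list in 3.1.7 is introduced as examples, so it might be read to include antiandrogens. Even then it governs use during PSA collection, not a rise after stopping.

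Several limits on the consequence stand. 7.6 calls the PSADT change exploratory, and section 11 plans no test of it. Arm A is observed untreated for two 4-week cycles with PSA and testosterone each cycle, which gives a concurrent reference and would reveal continuing recovery. After radiation, PSA must also exceed nadir + 2 ng/mL.

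A reader might infer more than the documents support:

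- **Bias between arms.** Randomisation spreads such men over both arms.
- **No stratification for prior hormone therapy.** Section 11.1 stratifies for prior therapy without defining it, so whether hormone therapy counts is not stated.
- **A man who stopped another antiandrogen a week ago is sure to qualify.** He still needs two rises above threshold and a PSADT in range, and his PSAs may be largely on-drug values.
- **Such men should be excluded as not castrate naive.** 3.1.7 deliberately admits men with past hormone therapy. Timing the PSAs makes their PSADT interpretable but does not change that choice.

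**Conclusion.** The gap is in the text, and 3.1.8, 3.1.10, 3.1.11 and 3.2.12 do not expressly close it. A PSA rise during testosterone recovery can satisfy the PSADT criterion and become the pre-study PSADT reference. Confidence is high on the wording and much lower on the consequences. The worked PSA and testosterone values are assumptions that show only that such a patient can enter, not how often he will.

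This is a question of population validity and of the within-patient PSADT comparison. A reader might infer a threat to the primary comparison from the steep dependence of type I error on the null rate. The documents do not support a size or even a direction, and the range in step 4 of the working shows only that the design is sensitive to the underlying rate.

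The amendment is worth making because the protocol already states the principle and the change is cheap. The conflict between 3.1.6 and 3.2.4 is minor, since an exclusion would normally govern, but it should not be left for sites to resolve.

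**What to change.** - In 3.1.7, extend the existing 3.1.6 condition: after any prior LHRH agonist, LHRH antagonist or antiandrogen, PSA2 and PSA3 (the values used for PSADT) must be drawn after a documented testosterone above 150 ng/dL that follows the last dose.
- For antiandrogens, also tie PSA2 and PSA3 to the end of therapy. The investigators should set and justify the interval, since the documents give no basis for choosing one across all antiandrogens. Reconcile the result with 3.2.12, which covers bicalutamide only.
- Reconcile 3.1.6 with 3.2.4 on experimental agents.
- State in section 11.1 what the prior-therapy stratum contains.
- Update the eligibility checklist to record the last dose date, the testosterone date and value, and the PSA2 and PSA3 dates.

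The cost is a wording amendment and a checklist change. Some men recently off hormone therapy would enter later. Others would need dated testosterone results or repeat PSAs, including some whose therapy ended long ago but who have no testosterone on record from before their PSA2. Limiting the rule to PSA2 and PSA3, and not the threshold PSA, keeps that burden down.

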2.0 OBJECTIVES

2.1 Primary endpoint:

The proportion of patients with undetectable PSA (< 0.2 ng/mL) at 32 weeks with metformin plus bicalutamide compared to bicalutamide monotherapy.

2.2 Secondary endpoints:

- The proportion of patients with PSA decline > 85% at 32 weeks with metformin plus bicalutamide compared to bicalutamide monotherapy.
- The time to PSA progression with metformin plus bicalutamide compared to bicalutamide monotherapy.
- To evaluate the time to onset of radiographic evidence of metastatic disease (rPFS) with metformin plus bicalutamide compared to bicalutamide monotherapy.
- To characterize the PSADT changes pre-study, during treatment, and off treatment.
- To evaluate the safety and tolerability of metformin in this patient population.
- To evaluate QOL with metformin plus bicalutamide compared to bicalutamide monotherapy.
- To evaluate the time to next therapy (i.e. antiandrogen or GnRH antagonist/agonist).

2.3 Exploratory endpoints:

- Immunogenicity of bicalutamide +/- metformin by flow cytometric analysis of T-cell frequency, activation status, cytokine profiles, antibody levels and analysis of sCD27 and sCD40L
- Evaluate circulating PSA levels and correlations with immunogenicity and/ or efficacy

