- PSA progression requires a PSA rise above the threshold measured at any time point since the threshold was reached.

3.1.11 PSA doubling time between 3 and 12 months. PSA calculation requires at least two consecutive PSA rises (PSA2 and PSA3) above the threshold PSA (at least 3 PSA values); PSA2 and PSA3 must be obtained within 12 months of study entry. All baseline PSAs should be obtained at the same reference lab. Patient's PSA doubling time must be calculated using the following formula (<http://www.mskcc.org/nomograms/prostate/psa-doubling-time>):

$$\text{PSADT in days} = \frac{0.693 (t)}{\ln (PSA3) - \ln (PSA2)}$$

Where t = the number of days between PSA3 and PSA2

ln = the natural log

PSADT in months = PSADT in days divided by 30.4375

3.1.12 ECOG performance status 0 to 2.

3.1.13 Ability to swallow the study drugs.

3.1.14 Subjects must have normal organ and marrow function as defined below:

- Absolute neutrophil count $\geq 1,000$ /mL
- Hemoglobin ≥ 10 g/dL
- Platelets $\geq 100,000$ /mL
- Total bilirubin within normal institutional limits
- AST(SGOT)/ALT(SGPT) ≤ 1.5 X institutional ULN
- Creatinine clearance ≥ 60 mL/min/1.73 m²
- Hgb A1c $\leq 6.5\%$

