11.0 STATISTICAL CONSIDERATIONS

11.1 Sample size

We will test the hypothesis that only 20% of patients on either arm of the study will have undetectable PSA at 32 weeks, versus the alternative that 40% of arm B patients will. An initial cohort of 39 patients and, if continued, a second cohort of 27 patients will be randomized 2:1 to arms B and A respectively.

After stratification for prior therapy we will randomize, 2:1, nominally 13 patients to arm A and 26 patients to arm B. Because of post stratification randomization, the exact numbers in the two arms may vary slightly from 13 and 26, but the total patient number in the the initial cohort will be exactly 39 and the final sample number be exactly 66. Our intent is to compare the proportions of patients with undetectable PSA at 32 weeks. This is most simply described by the difference $(E1/26) - (C1/13)$, where C1 and E1 are the numbers of undetectable PSAs in arms A and B respectively. The cut point for continuation of the trial past the first cohort requires that

$(E1/26) - (C1/13) > -2/13 = -0.1538462\dots$. To avoid confusion due to round off of such fractions, we identify the decision boundary by $13 E1 - 26 C1 > -52$, exactly equivalent the first expression, and obtained by multiplying all terms by $13*26$.

If $13 E1 - 26 C1$ exceeds -52 AND $E1$ is at least 6 then we will randomize an additional 9 patients to arm A and 18 patients to arm B. Otherwise the study will be terminated and the null hypothesis accepted. Letting $C2$ and $E2$ be the numbers of undetectable PSAs in the second cohort, we will finally reject the null hypothesis if $22(E1 + E2) - 44(C1 + C2)$ is at least 88 and $E1 + E2$ is at least 14. The initial cohort will consist of 39 and the final cohort of 27 patients for a total of 66 patients. If the true null is 20% undetectable PSAs type I error will be 3.24% and power will be 80.3%. In this case the chance of early stopping under the null will be 60% but will be 3.23% if the true arm B fraction of undetectable PSAs is 40%.

If the null (arm A) fraction undetectable PSAs is 25% type I error increases to 10.9% and power increases to 83.3% if the arm B fraction undetectable is 45% (20% higher). If the null fraction is 30% type I error increases to 19.7% and power to 83.2% (arm B 50%, 20% higher).

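### Eligibility can rest on PSA rises from before salvage therapy, with no minimum entry PSA, so a man already below 0.2 ng/mL can enrol and probably count as a primary-endpoint success

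*Combined protocol and SAP*

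**What the plan says.** The primary endpoint in section 2.1 is an absolute level: "The proportion of patients with undetectable PSA (< 0.2 ng/mL) at 32 weeks". It requires neither a detectable baseline nor a decline.

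The PSA eligibility rules in section 3.1 are:

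- 3.1.9: "PSA must be < 30 ng/mL at study entry". There is no lower limit.
- 3.1.10: "Patient must have evidence of biochemical failure after primary therapy and" subsequent progression. The anchor is primary therapy; salvage is not mentioned. On timing, "PSA progression requires a PSA rise above the threshold measured at any time point since the threshold was reached".
- 3.1.11: a doubling time of 3 to 12 months from two consecutive rises above the threshold, with "PSA2 and PSA3 must be obtained within 12 months of study entry". PSA3 need not be the latest value or post-date salvage.
- 3.1.5 admits men after curative-intent salvage: "Patient may have prior salvage therapy (surgery, radiation or other local ablative procedures) within 6 months prior to randomization".

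Among the exclusions, 3.2.5 bars "Radiation therapy within prior 6 months". Table 1 schedules a screening PSA, but no rule compares it with a minimum. Section 11.4 does not remove men who are undetectable at baseline.

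Section 11.1 ties the error rate to a 20% success rate: "If the true null is 20% undetectable PSAs type I error will be 3.24" per cent. It adds 10.9% at a 25% null rate and 19.7% at 30%, and says that type I error is below 5% for every possible split between the arms.

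**The concern.** The trial is meant for men with current biochemical recurrence. The criteria test for a past rise and never check that the recurrence is still present after the last local treatment. A man successfully salvaged after PSA3 has no current recurrence and already meets the endpoint level. He receives bicalutamide from cycle 3 in both arms, so he is likely still to be below 0.2 ng/mL at week 32 whether or not he takes metformin.

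The final rule uses fixed cut-offs: a minimum count in arm B and a minimum difference between the arms. Its false-positive rate climbs as the common success rate climbs. Men who succeed regardless of arm lift that rate, and they also narrow the achievable difference.

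The omission looks unintended. Section 3.1.6 requires the PSA rise and doubling time after neoadjuvant or adjuvant therapy to be documented once testosterone has recovered. No matching condition exists for salvage.

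**Working it through.** **Step 1. Can such a man pass?** Take this hypothetical case: prostatectomy, threshold 0.2 ng/mL reached, PSA2 of 0.30 at 11.5 months before entry, PSA3 of 0.45 at 8.5 months, salvage radiation finished 7 months before entry, screening PSA 0.08.

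- Doubling time by the 3.1.11 formula, with t = 91 days: 0.693 × 91 / ln(0.45/0.30) = 155.5 days. Divided by 30.4375 this is 5.1 months, inside 3 to 12.
- Both rises exceed 0.2 and fall within 12 months: 3.1.10 and 3.1.11 are met.
- 0.08 is below 30: 3.1.9 is met.
- Radiation ended more than 6 months earlier: 3.2.5 is not triggered.

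So even the strict reading of the radiation exclusion leaves a gap of roughly 6 to 12 months before entry. Salvage surgery and ablation have no time exclusion.

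**Step 2. Reproduce the design figures.** Inputs from 11.1: 13 (A) and 26 (B) in the first cohort, then 9 and 18 more. Continue if 13E1 − 26C1 > −52 and E1 ≥ 6. Reject the null if 22(E1+E2) − 44(C1+C2) ≥ 88 and E1+E2 ≥ 14. Exact enumeration of the four independent binomial counts gives:

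| Quantity | Stated | Computed |
|---|---|---|
| Type I error, null 20% | 3.24% | 3.246% |
| Power, 20% vs 40% | 80.3% | 80.36% |
| Early stopping, null 20% | 60% | 60.05% |
| Early stopping, 20% vs 40% | 3.23% | 3.236% |
| Type I error, null 25% | 10.9% | 10.98% |
| Type I error, null 30% | 19.7% | 19.70% |

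The plan's figures are reproduced; they are truncated rather than rounded.

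**Step 3. Add a share s of men who succeed in either arm.** The documents give no value for s, so it is an assumption shown as a range. Success rates become:

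- null rate, both arms: 0.20(1 − s) + s
- arm B under the alternative: 0.40(1 − s) + s
- difference: 0.20(1 − s)

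| s | Men of 66 | Null rate | Type I error | Difference (points) | Power |
|---|---|---|---|---|---|
| 0 | 0 | 20.0% | 3.25% | 20.0 | 80.4% |
| 1.5% | 1 | 21.2% | 4.7% | 19.7 | 80.8% |
| 2% | 1.3 | 21.6% | 5.2% | 19.6 | 80.9% |
| 5% | 3.3 | 24.0% | 9.1% | 19.0 | 80.8% |
| 10% | 6.6 | 28.0% | 16.5% | 18.0 | 79.0% |

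Type I error reaches 5% at s of about 1.8%, which is 0.018 × 66 = 1.2 men. One man in 66 leaves it at 4.7%.

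The plan's own sensitivity figures correspond to s = 0.05/0.80 = 6.25% (25% null) and s = 0.10/0.80 = 12.5% (30% null).

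**The case against.** The sponsor has four fair replies.

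- **The sensitivity is already disclosed.** Section 11.1 reports type I error at 25% and 30%, and every scenario above lies within that range. It would follow from any cause of a control rate above 20%. This stands: the fixed boundary is the source of the sensitivity. What 11.1 does not say is that the eligibility rules can themselves raise the rate.
- **Frequency is unsupported.** By the radiation route, both rises and the whole radiation course must fit between about 12 and 6 months before entry. An investigator must then enrol a man whose PSA has just fallen, in a trial titled for biochemical recurrence. Section 3.1.11 also speaks of baseline PSAs, which suggests current values. This stands as a reason to expect few such men. The wording suggests the intent but does not enforce it.
- **There is little loss of power.** Correct: at 2% and 5% power is slightly above its design value.
- **There is no arm bias.** Correct: such men enter both arms in expectation, and randomisation is stratified for prior therapy.

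A reader might infer three stronger things that the documents do not support. The first is that a single such man breaks the 5% limit; one in 66 gives 4.7%. The second is that he tells the trial nothing; he still contributes to safety, quality of life, time to PSA progression and onset of metastasis. The third is that the trial's type I error is in fact 9% or 16%; those values depend on an assumed share.

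**Conclusion.** The gap is in the text of 3.1.9 to 3.1.11, and neither 3.2.5 nor 11.4 closes it. The criteria can admit men who already meet the primary endpoint level. The main exposure is type I error, which goes from 3.25% to 4.7% with one such man in 66, passes the 5% stated in 11.1 at about 1.8%, and reaches 9.1% at a 5% share and 16.5% at 10%. Power stays between 79.0% and 80.9% over that range.

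These figures assume the nominal 13/26 and 22/44 splits, a true 20% rate among the other men, the same share s in both arms, and certain success for the men concerned. The last is probable, not guaranteed. The existence of the gap depends on none of these assumptions; its size depends on s, which is unknown.

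One side effect is certain for any such man. A decline of more than 85% from 0.08 ng/mL needs a week-32 value below 0.15 × 0.08 = 0.012 ng/mL, so the secondary PSA-decline endpoint becomes hard to interpret for him.

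**What to change.** Make two short changes to the eligibility text:

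- 3.1.9: add that screening PSA must be at or above 0.2 ng/mL, the endpoint's own cut-off.
- 3.1.11: require PSA2 and PSA3 to post-date the most recent local therapy, whether primary or salvage.

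A floor defined by the threshold for the man's prior therapy is not advisable. After prostatectomy plus salvage radiation it is unclear whether 0.2 ng/mL or nadir plus 2 ng/mL would apply, and those are the men at issue.

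Two neighbouring matters should be handled separately: 3.1.5 and 3.2.5 conflict on salvage radiation within 6 months and must be reconciled, and 3.1.10 gives no threshold after cryoablation, which 3.1.4 admits.

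The cost is a brief amendment. The PSA values and dates are already needed for the doubling-time calculation, and screening PSA is already scheduled. Some additional men will fail screening; the documents do not allow their number to be estimated.
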